9.4.3 Analysis of the Secondary Endpoint(s)

Frequencies and percentages for the secondary safety and tolerability endpoints will be determined using the ITT patient population for the non-blinded study phase and all randomized participants during the nonblinded study phase. Patients withdrawing prematurely from the study will be summarized by study timepoint and phase (blinded/non-blinded) and study arm (if applicable) and reason if available. The total number of adverse events (AE) will be summarized by severity, drug-relatedness, and whether it is an SAE and then also the total number of participants experiencing an AE will be summarized by study phase and/or study arm. Adherence to treatment regimen will be determined by the percentage of treatment ingested per the prescribed treatment amount at each evaluable study phase and by study arm during the blinded phase. The other secondary endpoint, incidence of the change in THI of 1 point or greater, will be summarized by study arm for those participants providing at least 1 post-week 3 baseline THI measurement.

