2.4 Potential Risks & Benefits

2.4.1.1 Known Potential Risks

Greater than minimal risk. Due to the risk of uterine contractions associated with oxytocin use, female subjects of childbearing potential will be instructed to use a double barrier of birth control and the PI will discuss with them the potential dangers if they were to become pregnant while using the drug. It is possible that high dose oxytocin may cause recruitment of vasopressin leading to a decrease in plasma and an increase in urine osmolality and a decrease in serum sodium levels. As a result, there is the less common risk of developing acute pulmonary edema. The main categories of side-effects include: feeling more calm, relaxed or comfortable, or having more energy (5%), drowsiness, lightheadedness or headaches (6%), and nasal irritation, dryness of the mouth or throat (3%). Patients with any serious adverse events will be immediately withdrawn from the study. However, because of the extremely short half-life of oxytocin, any adverse event would not be expected to be long-lasting.

There is the possibility of bruising from the needle site after blood draws at scheduled visits.

Subjects will be monitored with regular communication to note study challenges or adverse events. Individuals will work with study personnel who have been appropriately trained and access to data will be limited to an as needed basis. Information linking the linkage codes to participant's names, medical record numbers, and social security numbers will be stored in a secure location separate from the medical information and only accessible to members of the study team when needed, after approval by the NYU School of Medicine IRB and Principal Investigator. This access will be documented.

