4.2.1.2 Secondary and Exploratory Study Endpoints

Secondary endpoints will consist of safety and tolerability metrics including adverse event incidence and severity, regimen adherence and voluntary study drop-out rates reported during the non-blinded and blinded study phases. The frequency and percentage of each secondary measure will be determined for the non-blinded study phase and by study arm for blinded study phase. Additionally, any changes in THI greater than 1 grade will be determined from week 3 to week 6 of the double blinded study phase. The frequency and percentage of these changes will be summarized by study arm.

A descriptive summary using means and standard deviations stratified by dosage group for the treatment subgroup during the blinded study phase will be performed. The partial eta squared effect size difference will be estimated.

5 Study Enrollment and Withdrawal

Patients older than 18 years old are able to participate. The maximum age of participants is 75 years old. The racial and ethnic origin will reflect the demographics of the populations that seek evaluation of tinnitus at NYU Langone Medical Center.

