8.1 Specification of Safety Parameters

8.1.1 Definition of Adverse Events (AE)

An *adverse event* (AE) is any symptom, sign, illness or experience that develops or worsens in severity during the course of the study. Intercurrent illnesses or injuries should be regarded as adverse events. Abnormal results of diagnostic procedures are considered to be adverse events if the abnormality:

- results in study withdrawal
- is associated with a serious adverse event
- is associated with clinical signs or symptoms
- · leads to additional treatment or to further diagnostic tests
- is considered by the investigator to be of clinical significance

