8.3 Time Period and Frequency for Event Assessment and Follow-Up

The occurrence of an AE or SAE may come to the attention of study personnel during study visits and interviews of a study participant presenting for medical care, or upon review by a study monitor. All AEs including local and systemic reactions not meeting the criteria for SAEs will be captured on the appropriate RF. Information to be collected includes event description, time of onset, clinician's assessment of severity, relationship to study product (assessed only by those with the training and authority to make a diagnosis), and time of resolution/stabilization of the event. All AEs occurring while on study must be documented appropriately regardless of relationship. All AEs will be followed to adequate resolution.

Any medical condition that is present at the time that the participant is screened will be considered as baseline and not reported as an AE. However, if the study participant's condition deteriorates at any time during the study, it will be recorded as an AE. UPs will be recorded in the data collection system throughout the study.

Changes in the severity of an AE will be documented to allow an assessment of the duration of the event at each level of severity to be performed. AEs characterized as intermittent require documentation of onset and duration of each episode.

The PI will record all reportable events with start dates occurring any time after informed consent is obtained until 7 (for non-serious AEs) or 30 days (for SAEs) after the last day of study participation. At

each study visit, the investigator will inquire about the occurrence of AE/SAEs since the last visit. Events will be followed for outcome information until resolution or stabilization.

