9.2 Statistical Hypotheses

We hypothesize that treatment with high dose oxytocin nasal spray will result in a large effect size as measured by partial eta squared for the difference in mean area under the curve in baseline adjusted VAS when compared to placebo during the blinded study phase.

The primary outcome measurement will be the collective area under the VAS curve above the week 3 baseline as assessed from week 3 to week 6 of the blinded study phase. The area under the curve will be determined using the linear trapezoidal method for each participant after subtracting the baseline (week 3) VAS value from each subsequent measure to determine the collective improvement/decline of the VAS measurement during the blinded study phase. The mean and standard deviation of the total area will be

calculated for each study arm (active drug and placebo) and partial eta squared effect size for the difference determined. This effect size estimate can then be used to power future comparative studies.

The same area under the curve above the baseline VAS metric will be determined separately for the nonblinded/open label study phase. The inherent bias of non-blinding may influence this metric although the relatively larger sample size (n=30) could also improve precision. Therefore, the area will be presented as a descriptive summary using the mean and standard deviation with an effect size estimate.

Secondary endpoints will consist of safety and tolerability metrics including adverse event incidence and severity, regimen adherence and voluntary study drop-out rates reported during the non-blinded and blinded study phases. The frequency and percentage of each secondary measure will be determined for the non-blinded study phase and by study arm for blinded study phase. Additionally, any changes in THI greater than 1 grade will be determined from week 3 to week 6 of the blinded study phase. The frequency and percentage of these changes will be summarized by study arm.

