9.4.4 Safety Analyses

The total number of adverse events (AE) will be summarized by severity, drug-relatedness, and whether it is an SAE and then also the total number of participants experiencing an AE will be summarized by study phase and/or study arm.

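### Blinded-phase adverse events are compared only as totals, with no rule for events ongoing at randomisation and no table by event term, so persistence on oxytocin against resolution on placebo can go unseen

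*Combined protocol and SAP*

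**What the plan says.** Section 4.2.1.2 sets the secondary safety endpoints as "adverse event incidence and severity, regimen adherence and voluntary study drop-out rates reported during the non-blinded and blinded study phases". Section 9.2 repeats this and says that the frequency and percentage of each measure "will be determined for the non-blinded study phase and by study arm for blinded study phase". Section 9.3 takes all randomised participants as the blinded-phase safety set.

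Two AE summaries are planned. Section 9.4.4 says: "The total number of adverse events (AE) will be summarized by severity, drug-relatedness, and whether it is an SAE". Section 9.4.3 gives the same summary and adds that "the total number of participants experiencing an AE will be summarized by study phase and/or study arm". No table by event term or organ class is planned, and none of persistence or resolution.

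Section 8.1.1 defines an AE as "any symptom, sign, illness or experience that develops or worsens in severity during the course of the study". Under Section 8.3, at each visit "the investigator will inquire about the occurrence of AE/SAEs since the last visit". The same section collects times of onset and resolution, and states: "Changes in the severity of an AE will be documented to allow an assessment of the duration of the event at each level of severity". No section says which phase an AE belongs to if it began open-label and is ongoing at Visit 11, when randomisation takes place.

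Section 2.4.1.1 names specific risks: changes in sodium and osmolality, drowsiness, lightheadedness or headache, and nasal irritation or dryness. Of the fluid effects it says: "As a result, there is the less common risk of developing acute pulmonary edema".

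**The concern.** Everyone takes oxytocin for nine weeks before randomisation, so drug side effects in those who stay may well have begun before the arms exist. What randomisation can then show is whether an effect persists in those who continue and resolves in those switched to placebo. No planned table shows this, although the dates and severity changes needed are collected.

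Pooling is the second gap. One any-AE count merges the named risks with unrelated events. A difference confined to one event type is diluted, and a reader of the tables could not tell which event it was. The arm comparison in the blinded phase is the trial's only placebo-controlled safety evidence, and the larger study will draw on it.

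**Working it through.** **Inputs.** The plan gives no safety rate or precision target to reproduce. Its only design figure is n = 30 (Section 9.5), randomised half to each arm (Section 4.1): 30 / 2 = 15 per arm. Section 2.1 cites a review in which 18% of 1529 participants, 926 of them on oxytocin, reported mild side effects. I borrow 18% as the share q with an AE ongoing at randomisation; this is an assumption. A new-onset rate b of 0 or 10%, equal in both arms, is also assumed.

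**Counting rules.** Take a continuous AE of unchanged severity that persists in all affected participants on oxytocin and resolves within two weeks in all affected participants on placebo. New-onset AEs are taken to be present in the later blinded weeks.

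- Onset in phase: 15b in each arm.
- Present at any time in phase: 15[1 − (1 − q)(1 − b)] in each arm, because placebo participants still have the AE when the phase begins.
- Present from blinded week 3: 15[1 − (1 − q)(1 − b)] on oxytocin, 15b on placebo.

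At q = 0.18, 15 × 0.18 = 2.7. With b = 0.10, 15 × (1 − 0.82 × 0.90) = 15 × 0.262 = 3.9.

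| Rule | b = 0, oxytocin v placebo | b = 10%, oxytocin v placebo |
|---|---|---|
| Onset in phase | 0 v 0 | 1.5 v 1.5 |
| Any time in phase | 2.7 v 2.7 | 3.9 v 3.9 |
| From blinded week 3 | 2.7 v 0 | 3.9 v 1.5 |

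Both natural readings of the planned count give equal arms. Only the third rule separates them, and the safety sections do not state it. Section 9.4 does say that blinded-phase data collection starts at week 3 of the phase, but in its text on the efficacy washout; Sections 7.2.3.10 and 7.2.3.11 record AEs at Visits 12 and 13, inside those first two weeks.

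**Range.** The hidden difference is q × (fraction persisting on oxytocin − fraction persisting on placebo).

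- All persist on oxytocin, none on placebo: 18 points.
- A quarter persist on oxytocin, none on placebo: 0.18 × 0.25 = 4.5 points.
- Equal persistence in both arms: 0.

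At q = 6% (drowsiness, lightheadedness or headache, Section 2.4.1.1) the ceiling is 6 points, or 0.9 of 15.

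**Pooling.** Suppose one harm occurs in 20% v 0% and independent other AEs affect 40% of each arm (assumptions). The any-AE rates are 1 − 0.80 × 0.60 = 52% v 40%, so 20 points become 12. With other AEs at 60%, they are 1 − 0.80 × 0.40 = 68% v 60%, or 8 points.

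**What 15 per arm can show.** At 18% v 0%, the chance of at least one oxytocin case is 1 − 0.82^15 = 0.95, but the power of a two-sided 5% Fisher test is only 0.12. It is 0.49 at 30% v 0% and 0.78 at 40% v 0%.

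**The case against.** A reader might infer that the plan counts AEs by onset and so must show no arm difference. The documents do not say that. The question about events since the last visit in Section 8.3 is a collection prompt, and no section assigns a carried-over AE to a phase. The rule is unstated.

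Equal arms also need a continuous AE of unchanged severity. Section 8.1.1 makes worsening an AE, Section 8.3 documents each episode of an intermittent one, and event totals are planned beside participant counts. With a plasma half-life of 3–17 minutes (Section 2.1) and dosing four times daily, episodic effects are plausible, and counted by episode they could separate the arms.

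The 18% is not a forecast. It pools active and placebo recipients, and the review reports a nearly 1:1 ratio between them. The placebo also shares the vehicle (Section 6.1), so irritation caused by the vehicle would not resolve on switching. Against this, Section 2.1 also describes a 12-patient trial at 160 IU/day, within this trial's 120–180 IU/day range, with mild dizziness in four oxytocin patients and none mentioned on placebo. Zero is therefore not assured either.

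Nor would the named harms appear only inside a total. SAEs are split out, withdrawals are summarised by arm and reason, urine sodium or osmolality abnormalities lead to withdrawal (Section 6.1.8), and further pulmonary oedema is reported to the IRB (Section 8.6).

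Finally, Sections 9.1 and 9.4.1 place initial safety and tolerability estimation in the open-label phase, where AEs that begin on oxytocin are counted. All these points stand and limit the concern. They do not remove it, because Sections 4.2.1.2 and 9.2 still promise AE results by arm in the blinded phase.

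**Conclusion.** The point holds in a limited form. The blinded-phase safety comparison lacks a rule for AEs ongoing at randomisation and any breakdown by event term. For a continuous, unchanged AE, both obvious ways of counting participants hide persistence on drug against resolution on placebo.

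The size is unknown: from about 0 to a ceiling of 18 percentage points (2.7 of 15). The ceiling assumes that 18% have such an AE at randomisation, that all persist on oxytocin and that all resolve on placebo. The gap mainly concerns non-serious AEs that do not lead to withdrawal.

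It would go too far to conclude that the trial's overall tolerability findings will be too favourable: the open-label phase counts these AEs, and serious events and withdrawals are visible separately. With 15 per arm the comparison is descriptive either way. This is an inexpensive improvement to make before data lock.

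**What to change.** In Sections 9.4.3 and 9.4.4, add for the blinded phase, by randomised arm and event term:

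- (a) participants with the AE present after the first two blinded weeks, including AEs that began open-label;
- (b) among AEs ongoing at Visit 11, the number resolved, unchanged or worsened by Week 15;
- (c) new-onset AEs, with a note that this comparison applies to participants who tolerated open-label drug.

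Show the risks named in Section 2.4.1.1 as separate rows in both phases.

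Also reconcile the safety set. Sections 9.4 and 9.4.3 place the summary of all randomised participants in the non-blinded phase, while Section 9.3 places it in the blinded phase.

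The cost is SAP wording and a few descriptive tables built from AE terms, dates and severity changes already collected. No visit, procedure or treatment rule changes. The downside is more tables with small counts, which should be read as description and not tested.

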2.4.1.2 Known Potential Benefits

Subjects may or may not directly benefit from being in the study. Close medical monitoring of their symptoms may be a potential benefit if subjects are seen infrequently otherwise. Furthermore, if the medication is effective for tinnitus, participants may indeed improve. However, the overall benefit of participating in this research is that it may help others with tinnitus in the future.

3 Objectives and Purpose

The purpose of this study is to evaluate the effects of high-dose intranasal oxytocin for treating tinnitus.

The primary outcome measurement will be a change in the VAS at 3 timepoints:

1. Comparative endpoint of VAS of all 30 subjects at 9th week of treatment with active drug vs baseline.

2. Comparative endpoint during the cross-over phase of VAS at the 17th visit (15th week of study) between the 15 subjects who received placebo vs the 9th week of the non-blinded phase for the same subjects (when they were on active drug). This endpoint compares the 15 patients that were switched from active to placebo and compares their response on placebo (from the double blind phase) with their response on active drug (from the non-blinded phase) and compares them to the 15 subjects that remained on active drug during the entire study.

3. A parallel group analysis where we compare both arms in the last week of the double-blind phase—so in essence we are comparing those 15 who were on active throughout the entire study to those that started on active and changed over to placebo.

Secondary endpoints of interest are also defined a-priori:

1. A change in the THI by at least one grade contrasting the 9th week (end of the single blinded phase) and the 15th week of the study (end of the double blinded phase) between the 15 subjects who were switched from active drug to placebo.

2. A change in the THI by at least one grade during the last 2 weeks of the double-blind stage (weeks 14 and 15 of the study contrasting those on active drug vs. placebo.

Exploratory endpoints of interest include:

Clinical Global Impression (CGI) measured following the same approach of the primary endpoints. Tinnitus Functional Index (TFI) measured following the same approach of the primary endpoints.

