5.2 Exclusion Criteria

An individual who meets any of the following criteria will be excluded from participation in this study:

- 1. Treated for tinnitus < 6 months due to the acute nature of their condition and slight handicap according to the Tinnitus Handicap Inventory Severity Scale.
- 2. Tinnitus of a muscular or vascular etiology
- 3. Conductive hearing loss
- 4. History of migraine
- 5. History of pulmonary edema
- 6. History of congestive heart failure
- 7. History of severe renal disease
- 8. Prior use of oxytocin nasal spray
- 9. Latex allergy
- 10. Women who are currently breastfeeding
- 11. Pregnancy

Because tinnitus may be co-morbid with migraine, and because migraine may be responsive to treatment with intranasal oxytocin, patients who suffer from migraines will be ineligible to participate. As patients who are allergic to latex may react to the oxytocin spray, individuals with this allergy will be ineligible to participate in the study.

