9.4 Description of Statistical Methods

Data from this pilot study will be summarized separately for the non-blinded study phase and by study arm for the blinded study phases. The area under the VAS curve after subtracting baseline value will be determined using the linear trapezoidal method. These areas will be determined for the efficacy population using the last observation carried forward (LOCF). The mean and standard deviation for the non-blinded phase will be determined and the effect size for the mean area from zero calculated. For the blinded phase week 3 (after a 2 week "washout") will serve as the baseline and the area under the VAS curve from baseline will be calculated using LOCF imputation for missing post baseline data. To avoid potential cross-over effects from the 9 week non-blinded phase when all subjects receive active drug, after randomization, subjects will receive either active drug or placebo. The first 2 weeks of this 6 week period will be a washout period from statistical analysis. While subjects will still receive study drug, data collection for that phase will not begin until week 3 of that 6 week period. The mean and standard deviation in area under the VAS curve from baseline for each study arm will be determined and the partial eta effect size for the mean difference between study arms calculated. This summary will be performed for the per protocol study population as well to investigate the relative influence of missing data on the effect size determination.

Frequencies and percentages for the secondary safety and tolerability endpoints will be determined using the ITT patient population for the non-blinded study phase and all randomized participants during the nonblinded study phase. The other secondary endpoint, incidence of the change in THI of 1 point or greater, will be summarized by study arm for those participants providing at least 1 post-week 3 baseline THI measurement.

The analyses will be refined and adjusted in anticipation of study termination and data lock.

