9.4.1 General Approach

The study design is a pilot, proof of concept, two-phase study. The first non-blinded study phase is to provide tolerability, regimen adherence, and initial safety data for the active treatment. The second phase after 2 week washout allows for efficacy comparison of the mean VAS difference from baseline between

active drug and placebo and incidence of THI changes greater than 1 point. Please see Schematic of Study Design.

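### Counting THI changes of 1 point or more, in either direction, mostly counts measurement error, and Section 9 plans no analysis of the THI score itself

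*Combined protocol and SAP*

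**What the plan says.** The documents define the THI event in four ways.

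- **1 point or more:** Section 9.4.3, "The other secondary endpoint, incidence of the change in THI of 1 point or greater, will be summarized by study arm", with the same rule in Section 9.4, "incidence of the change in THI of 1 point or greater, will be summarized by study arm".
- **More than 1 point:** Section 9.4.1, "incidence of THI changes greater than 1 point".
- **More than 1 grade:** Section 4.2.1.2, "any changes in THI greater than 1 grade will be determined from week 3 to week 6 of the double blinded study phase", and Section 9.2, "any changes in THI greater than 1 grade will be determined from week 3 to week 6 of the blinded study phase".
- **At least one grade:** Section 3, "A change in the THI by at least one grade contrasting the 9th week" and "A change in the THI by at least one grade during the last 2 weeks of the double-blind stage".

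Sections 9.4 and 9.4.3 include anyone with one THI reading after the week 3 baseline. They give no direction, no confirming reading and no allowance for measurement error. The planned output is a frequency and percentage by arm.

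Other scales are treated differently. VAS area gets means, SDs and an effect size (9.4.2), and CGI and TFI change get means and SDs (9.4.7.6). The Protocol Summary and Section 4.1 mention THI improvement at p < 0.10, but name no test or form of outcome, and Section 9 does not take the criterion up. Section 4.1 calls the secondary metrics exploratory and says the results will guide the next, larger study.

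The visit lists in Section 7.2 name THI at study Weeks 9, 11, 13 and 15.

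**The concern.** A questionnaire score varies from one sitting to the next even when the patient is unchanged. A cut of 1 point will usually lie inside that variation, so an event need not mean that anything has happened. Because no direction is given, worsening counts as well as improvement. If one arm improved and the other worsened by the same amount, the expected event rates would be identical.

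Two things would be lost: a readable THI comparison between the arms, and a THI mean difference and SD for planning the next study. Section 9.5 gives effect-size estimation for that study as the trial's main goal.

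**Working it through.** **Figures in the plan.** There is nothing to reproduce. Section 9.5 gives n = 30 (15 per arm at 1:1) without a calculation, and no THI event rate, SD, margin or power is stated.

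**Inputs.** From the documents: 15 per arm, the four event rules, and the p < 0.10 level named for the secondary scales. Assumed, because the documents give none of them: the error SD of one THI reading (s), the scoring step, the grade width and the true difference.

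**Step 1: noise-only rate for the 1-point rule.** With no true change, the difference between two readings has SD √2·s, so

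P(|change| ≥ 1) = 2·[1 − Φ(1/(√2·s))].

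For s = 3: 1/4.243 = 0.236 and Φ = 0.593, which gives 81%. The same rate is expected in both arms.

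| s (points) | Formula | Simulated, scores rounded to 2-point or 1-point steps |
|---|---|---|
| 1 | 48% | 51% or 73% |
| 2 | 72% | 73% or 86% |
| 3 | 81% | 81% or 90% |
| 5 | 89% | 88% or 94% |
| 10 | 94% | 93% or 96% |

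The formula reaches 50% when 1/(√2·s) = 0.6745, that is, s = 1.05. Counting improvement only halves the rate: 36% to 47% for s from 2 to 10.

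The rule in Section 9.4.1 (more than 1 point) behaves in much the same way. With 2-point steps it is the same rule. With 1-point steps it means at least 2 points, roughly 2·[1 − Φ(1.5/(√2·s))]: for s = 3, 2·[1 − Φ(0.354)] = 72%.

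**Step 2: noise-only rates for the grade rules (simulated).**

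- At least one grade: 16% to 46% for s from 3 to 7 and grade widths of 15 to 25 points. A second simulation, with s from 3 to 8 and widths of 16 to 24, gave 15% to 51%, or 7% to 26% for improvement only.
- More than 1 grade: 0% to 3% for s from 3 to 7, and 2% to 11% at s = 10.

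**Step 3: what the count gives up.** Assume 15 per arm, two-sided 10%, one arm stable and the other shifted by a fixed true difference, with error as the only source of variance (normal approximation). For s = 5 and a difference of 7, the SD of change is 7.07 and the standard error of the arm difference is 7.07·√(2/15) = 2.58. Then 7/2.58 = 2.71 and power = Φ(2.71 − 1.645) = 86%.

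| s, true difference | Mean THI change | 1-point count, either direction | 1-point count, improvement only |
|---|---|---|---|
| 5, 7 | 86% | 11% (events 89% v 93%) | 66% (44% v 80%) |
| 5, 10 | 99% | 18% (89% v 96%) | 87% (44% v 90%) |
| 10, 10 | 61% | 7% (94% v 96%) | 44% (47% v 74%) |

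Fisher's exact test on the either-direction count does worse still: 3%, 4% and 1%. All these powers are optimistic in absolute terms; the comparison across columns is what matters.

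**Step 4: which readings exist.** Randomisation is at study Week 9, so blinded week 3 is study Week 9 + 3 = 12 and blinded week 6 is Week 15. The Week 12 contact (Visit 14) is a phone call for which Section 7.2.3.12 names only the TFI. The schedule tables tick questionnaires at every visit without saying which. THI is named at Weeks 9 and 15.

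**The case against.** The strongest reply is that the event rates near 90% come from a wording conflict. Sections 3, 4.2.1.2 and 9.2 speak of grades, and the endpoint in 9.4.3 is evidently meant to be the one those sections define. If the conflict is settled in favour of grades, those rates disappear. This stands in part. A reader might infer that every THI rule in the plan makes most participants events, and the documents do not support that: noise gives a minority under at least one grade in nearly every scenario, and almost no events under more than 1 grade. But 9.4 and 9.4.3 are the sections an analyst would follow, and settling on grades would still leave no score analysis.

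A reader might also infer that each participant has two chances to be counted. The inclusion condition says who is analysed, not that a change at any visit counts. Sections 4.2.1.2 and 9.2 specify week 3 to week 6, and the Week 12 visit list names no THI.

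The power figures do not describe a planned test, since 9.4.3 is descriptive. They also assume the same true effect in everyone. In a separate run (two-sided 5%, 8-point difference), a between-person SD of 10 points in true change cut the power of the baseline-adjusted score analysis to 38% at s = 5 and 28% at s = 8. The score analysis still beat the count, but 15 per arm cannot be relied on to show a THI effect.

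Finally, the endpoint is exploratory and success is judged on VAS alone. That limits the harm. It does not make a rate near 90% in both arms useful for planning.

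**Conclusion.** The concern holds for the point wording in Sections 9.4, 9.4.1 and 9.4.3. Under assumed error SDs of 3 to 10 points, about 81% to 96% of participants would be 1-point events in both arms with no treatment effect. Only an error SD of about 1 point or less would bring the rate down to half.

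Section 9 has no THI score analysis to fall back on, and the p < 0.10 criterion has no planned test behind it.

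The consequence is an uninformative exploratory secondary result and no THI effect size for the next study. A reader might go further and suspect the primary conclusion; nothing supports that, because it rests on the VAS area. Error SD, scoring step, grade width and true difference are all assumptions.

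**What to change.** In Section 9.4.3, with matching edits in 4.2.1.2, 9.2, 9.4 and 9.4.1:

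- Make the main THI analysis the between-arm difference in THI total score at Week 15, adjusted for the Week 9 pre-randomisation score in a linear model. Report it with a confidence interval and with means and SDs by arm.
- Drop the 1-point count.
- Keep one grade-change percentage as supporting description, with a single reconciled threshold and a stated direction.
- Either link the p < 0.10 criterion in the Protocol Summary and Section 4.1 to this model or remove it for THI.

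Both readings are already scheduled, and the change avoids Week 12, where no THI is listed. The cost is SAP wording and one linear model, and Section 9.4 already allows the analyses to be refined before data lock.

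The downsides are real but modest. The headline THI result becomes a mean difference rather than a percentage. Its baseline is Week 9, not the week 3 baseline used for VAS, so the contrast takes in the first two blinded weeks that the VAS analysis leaves out. The interval at 15 per arm will be wide.
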